5.0 SUBJECT SELECTION AND WITHDRAWAL

5.1 Subject Population

Subjects enrolled into this clinical investigation will be male and female subjects derived from the general interventional cardiology population. The clinical investigation will register up to 107 subjects, with a maximum of two *de novo* coronary artery lesions (among them, only one target lesion is allowed and must be treated by an ABT NG DES 48, the other lesion must be a non-target lesion and be treated by stents other than the ABT NG DES 48) in separate epicardial coronary vessels. Subjects must meet all eligibility criteria and provide written informed consent prior to conducting any investigation-specific procedures that are not considered standard of care at the site.

5.2 Subject Screening and Informed Consent

5.2.1 Subject Screening

Subjects planned to be admitted for a percutaneous coronary artery revascularization procedure should be screened for clinical investigation eligibility by a member of the research team previously trained to the CIP.

Clinical Investigation Plan

Subjects have signed an Informed Consent form (ICF) (Refer to **Section 5.4, Subject Enrollment and Point of Registration**) are considered enrolled in the SPIRIT 48 study. An informed consent form has to be signed prior to the index procedure of the clinical investigation.

Subject data will be collected following enrollment into the clinical investigation.

5.2.2 Informed Consent

The Investigator or his/her authorized designee (if applicable) will conduct the Informed Consent process, as required by applicable regulations and the site's IRB/EC. This process will include a verbal discussion with the subject on all aspects of the clinical investigation that are relevant to the subject's decision to participate, such as details of clinical investigation procedures, anticipated benefits, and potential risks of clinical investigation participation. Subjects must be informed about their right to withdraw from the clinical investigation at any time and for any reason without sanction, penalty or loss of benefits to which the subject is otherwise entitled. Withdrawal from the clinical investigation will not jeopardize their future medical care or relationship with the investigator.

During the discussion, the Principal Investigator or his/her authorized designee will avoid any improper influence on the subject and will respect subject's legal rights. Financial incentives will not be given to the subject. Subjects may be compensated for time and travel directly related to the participation in the clinical investigation. The subject shall be provided with the Informed Consent form written in a language that is understandable to the subject and has been approved by the center's IRB/EC. The subject shall have adequate time to review, ask questions, and consider participation. The Principal Investigator or his/her authorized designee will make efforts to ensure that the subject understands the information provided. If the subject agrees to participate, the Informed Consent form must be signed and dated by the subject and thereafter by the person obtaining the consent prior to any clinical investigation-specific procedures. The signed original will be filed in the subject's hospital or research charts, and a copy will be provided to the subject.

Failure to obtain informed consent from a subject prior to clinical investigation enrollment should be reported to Sponsor within 5 working days and to the reviewing center's IRB/EC according to the IRB's/EC's reporting requirements.

If, during the clinical investigation, new information becomes available that can significantly affect a subject's future health and medical care, the Principal Investigator or his/her authorized designee (if applicable) will provide this information to the subject. If relevant, the subject will be asked to confirm their continuing informed consent in writing.

5.2.2.1 Special Circumstances for Informed Consent

Incapacitated individuals, defined as persons who are mentally ill, mentally handicapped, or individuals without legal authority, are excluded from the study population.

Individuals unable to read or write may be enrolled in this clinical investigation. Informed consent will be obtained through a supervised oral process. An independent witness will be present throughout the Informed Consent process. The written Informed Consent form and any other information will be read aloud and explained to the prospective subject or his/her legally acceptable representative and either will sign and personally date the Informed Consent form. The witness will also sign and personally date the

Clinical Investigation Plan

Informed Consent form attesting that the information was accurately explained, and that informed consent was freely given.

Pregnant or breastfeeding women are excluded from the study population.

All other aspects of the Informed Consent process will be in compliance with **Section 5.2.2**.

In addition, an authorization for use and disclosure of the subject's protected health information, in accordance with the Health Insurance Portability and Accountability Act (HIPAA), must be obtained from the subject or their legally acceptable representative (US subjects only).

For live cases at congresses, the subjects need to sign a specific Live Case ICF, approved by the IRB/EC and by the Sponsor, as well as by the competent authorities (e.g., FDA, or local IRB/EC), as applicable. The investigator must request Sponsor approval prior to performing a live case.

5.3 Eligibility Criteria

5.3.1 General Eligibility Criteria

Assessment for general eligibility criteria is based on medical records of the site and interview with a candidate subject. If some of the clinical or laboratory tests are not included in site standard tests or subject's medical record, they must be done after written informed consent is obtained. Subjects must meet ALL of the eligibility criteria to be considered for the clinical investigation.

5.3.2 Inclusion Criteria

5.3.2.1 General Inclusion Criteria

1. Subject must be at least 18 years of age.
2. Subject or a legally authorized representative must provide written informed consent prior to any study related procedure, per site requirements.
3. Subject must have evidence of myocardial ischemia (e.g., unstable angina, post-infarct angina, stable angina or silent ischemia) suitable for non-emergent PCI. Subject with stable angina or silent ischemia must have objective sign of ischemia as suggested by one of the following:
 - Abnormal stress or imaging stress test
 - Abnormal computed tomography-fractional flow reserve (CT-FFR)
 - Stenosis by visual estimation $\geq 70\%$
 - Abnormal pressure-derived indexes (FFR, instantaneous wave-free ratio [iFR], or relative flow reserve [RFR])
4. Subject must be an acceptable candidate for coronary artery bypass graft (CABG) surgery.

Clinical Investigation Plan

5. Subject must agree not to participate in any other clinical study for a period of one year following the index procedure.

5.3.2.2 Angiographic Inclusion Criteria

1. Only one *de novo* target lesion in native coronary artery is allowed to be treated with the investigational stent.
 - One additional non-target lesion can be treated if it is located in a different epicardial coronary vessel and NOT in left main coronary artery. The non-target lesion must be treated first and must be deemed an angiographic success.
2. The target lesion must be located in a native coronary artery with:
 - Visually estimated reference vessel diameter (RVD) of ≥ 2.5 mm and ≤ 4.25 mm.
 - Visually estimated lesion length of > 32 mm and ≤ 44 mm, and able to be covered by a single ABT NG DES 48
 - Multiple focal *de novo* lesions in an epicardial coronary vessel are allowed if the lesions can be covered by one stent. Multiple focal *de novo* lesions will be counted as a single lesion.
 - Visually estimated diameter stenosis of $> 50\%$ and $< 100\%$ with a Thrombolysis in Myocardial Infarction (TIMI) flow of ≥ 1
 - Stable angina or silent ischemia subjects must have stenosis $\geq 70\%$, or abnormal pressure-derived physiological indices (FFR, iFR, or RFR), unless abnormal stress or imaging stress test is evidenced

5.3.3 Exclusion Criteria

5.3.3.1 General Exclusion Criteria

1. Subject has known hypersensitivity or contraindication to device material and its degradants (everolimus, cobalt, chromium, nickel, tungsten, acrylic and fluoropolymers, etc.), or has known contrast sensitivity.
2. Subject has known hypersensitivity or contraindication to aspirin, heparin/bivalirudin, P2Y12 inhibitors (clopidogrel /prasugrel /ticagrelor), and therefore cannot be adequately pre-medicated.
3. Subject has a planned surgery or procedure necessitating discontinuation of aspirin or P2Y12 inhibitor within 12 months following index procedure.
4. Subject is receiving or will require chronic anticoagulation therapy (e.g., coumadin, dabigatran, apixaban, rivaroxaban or any other agent for any reason).

Clinical Investigation Plan

5. Pregnant or nursing subjects and those who plan pregnancy in the period up to 1 year following index procedure. Female subjects of child-bearing potential must have a negative pregnancy test done within 7 days prior to the index procedure per site standard test.
6. Subject had an acute myocardial infarction (AMI) within 48 hours of the index procedure with either of the situations below:
 - The subject is currently experiencing clinical symptoms consistent with new onset AMI, such as nitrate-unresponsive prolonged chest pain with ischemic electrocardiogram (ECG) changes
 - Elevated cardiac biomarker values have not returned to within normal limits at the time of index procedure.
7. Subject has a left ventricular ejection fraction (LVEF) < 30% within 3 months prior to the index procedure, that was documented by any method.
8. Subject is expected to require percutaneous mechanical cardiac support at the index procedure.
9. Prior PCI within the target vessel during the last 12 months prior to consent.
10. Prior PCI within the non-target vessel or any peripheral intervention during the last 30 days prior to consent.
11. At the index procedure, subject is identified to require planned stenting procedure (including staged procedures) or CABG after the index procedure.
12. Subject has received a solid organ transplant which is functioning or is active on a waiting list for any solid organ transplants with expected transplantation within 24 months.
13. Subject has a malignancy that is not in remission.
14. Subject is receiving immunosuppressant therapy or has known life-threatening immunosuppressive or severe autoimmune disease (e.g., human immunodeficiency virus, systemic lupus erythematosus, etc.). Note: corticosteroids are not included as immunosuppressant therapy, diabetes mellitus is not regarded as autoimmune disease
15. Subject has previously received or is scheduled to receive radiotherapy to a coronary artery (vascular brachytherapy), or the chest/mediastinum.
16. Subject has a platelet count < 100,000 cells/mm³ or > 700,000 cells/mm³.

Clinical Investigation Plan

17. Subject has renal insufficiency as defined as an estimated glomerular filtration rate (GFR) < 30 ml/min/1.73m² or dialysis at the time of consent^e.
18. Subject is high risk of bleeding for any reason; has a history of bleeding diathesis or coagulopathy; has had a significant gastro-intestinal or significant urinary bleed within the past six months.
19. Subject has had a cerebrovascular accident or transient ischemic neurological attack (TIA) within the past 6 months, or any prior intracranial bleed, or any permanent neurologic defect, or any known intracranial pathology (e.g. aneurysm, arteriovenous malformation, etc.).
20. Subject has extensive peripheral vascular disease that precludes safe 6 French sheath insertion. Note: femoral arterial disease does not exclude the subject if radial access may be used.
21. Subject has life expectancy < 2 years.
22. Subject is, in the opinion of the Investigator or designee, unable to comply with the requirements of the study protocol or is unsuitable for the study for any reason. This includes completion of Subject Reported Outcome instruments.
23. Subject is currently participating in another clinical investigation (except for non-invasive observational studies) that has not yet completed its primary endpoint.
24. Subject intends to participate in another investigational drug or device clinical investigation (except for non-invasive observational studies) within 12 months after the index procedure.
25. Subject has other medical illness (e.g., cancer or congestive heart failure) or known history of substance abuse (alcohol, cocaine, heroin etc.) that may cause non-compliance with the protocol, confound the data interpretation or is associated with a limited life expectancy less than 2 year.
26. Presence of other anatomic or comorbid conditions, or other medical, social, or psychological conditions that, in the investigator's opinion, could limit the subject's ability to participate in the clinical investigation or to comply with follow-up requirements, or impact the scientific soundness of the clinical investigation results.
27. Subject has active symptoms and/or a positive test result of COVID-19 or other rapidly spreading novel infectious agent within the prior 2 months.

Angiographic Exclusion Criteria:

1. Target lesion/vessel meets any of the following criteria:
 - Prevents complete angioplasty balloon (plain old balloon angioplasty [POBA], scoring balloon, or cutting balloon) inflation, such as:

^e Estimated GFR can be based on Modification of Diet in Renal Disease (MDRD) equation or Cockcroft-Gault equation (CCG).

Clinical Investigation Plan

- Heavy calcified lesion
 - Requires additional device for lesion preparation (e.g., rotablator or laser)
 - Anatomy proximal to or within the lesion that prevents proper placement of delivery system:
 - Extreme angulation ($\geq 90^\circ$) proximal to or within the target lesion
 - Excessive tortuosity (\geq two 45° angles) proximal to or within the target lesion
 - Involves a bifurcation of which the side branch will be jailed by the struts and requiring side branch pre-dilatation by Kissing Balloon Technique, and/or stenting.
 - Is located:
 - In left main or there is a $\geq 30\%$ diameter stenosis in the left main (unless the left main lesion is a protected left main (i.e. a patent bypass graft to the LAD and/or LCX arteries is present), and there is no intention to treat the protected left main lesion.
 - Within 3 mm of the origin of the LAD or LCX.
 - Within 3 mm of aorto-ostial RCA.
 - In a bypass graft or distal to anastomotic site of bypass graft.
 - With total occlusion (TIMI flow 0), prior to crossing with the wire.
 - Contains thrombus.
 - The subject has been previously treated with a stent within 1-year prior to the index procedure such that the ABT NG DES 48 would need to cross the stent to reach the target lesion.
2. Unsuccessful target lesion pre-dilatation, defined as the presence of one or more of the following:
- Failed for a full inflation of the pre-dilatation balloon.
 - TIMI flow grade < 3 (per visual estimation).
 - Any angiographic complication (e.g. distal embolization, no-reflow).
 - Any dissection National Heart, Lung, and Blood Institute (NHLBI) grade D-F.
 - Any chest pain lasting > 5 minutes.
 - Any ST-segment depression or elevation lasting > 5 minutes.
 - Side branch requires additional dilatation/stenting caused by plaque shift, carina shift or may require additional dilatation/stenting after stent implantation, per the operator's assessment.

Clinical Investigation Plan

3. Non-target lesion meets any of the following criteria:
 - Is located in the target vessel
 - Is located in the left main location
 - Is restenotic from a previous stent implantation
 - Is located within a saphenous vein graft or an arterial graft
 - Is with a TIMI flow 0 (total occlusion) prior to guide wire crossing
 - Involves a complex bifurcation that needs two-stent strategy
4. Treatment of non-target lesion is not deemed successful.
 - Note: A successful treatment is defined as a treatment resulted in a mean lesion diameter stenosis < 30% in 2 near-orthogonal projections with TIMI 3 flow, as visually assessed by the physician, without the occurrence of prolonged chest pain or ECG changes consistent with MI.

5.4 Subject Enrollment and Point of Registration

A subject is considered enrolled in the clinical investigation from the moment the subject provides written informed consent.

The point of registration is when an ABT NG DES 48 is started to be delivered beyond the tip of the guide catheter, entering into a subject's vasculature.

A subject who is enrolled but not registered into this study will be considered as a screen failure. If an enrolled subject is not found meeting general eligibility criteria prior to the index procedure, or not meeting angiographic eligibility criteria during the index procedure, the subject should not be registered and should be considered as a screen failure.

5.4.1 Enrollment of Medicare Beneficiaries (US only)

This section is only applicable to sites enrolling subjects in the United States.

This clinical investigation will enroll Medicare beneficiaries that qualify based on the inclusion and exclusion criteria defined for this clinical investigation. This IDE clinical investigation conforms to all standards of Medicare coverage requirements. The **Risk Analysis (Section 15)** describes how all enrolled subjects, including Medicare beneficiaries, may be affected by the device under investigation.

A portion of the subjects enrolled in the clinical investigation display characteristics consistent with the Medicare population based on age or gender. The clinical investigation results will be analyzed by age (< 65 years and ≥ 65 years) or by gender and compared to ensure that the outcomes are similar between the Medicare and non-Medicare populations.

Clinical Investigation Plan

5.4.2 Historically Under-Represented Demographic Subgroups

Abbott intends to implement FDA's guidance on sex-specific data in medical device clinical investigations to ensure adequate representation of women and other traditionally under-represented demographic subgroups in this clinical investigation. As noted in the guidance, some barriers to participation of women and ethnic minorities in clinical investigations have traditionally been:

- Lack of understanding about main obstacles to participation of such subgroups in clinical research
- Inclusion/exclusion criteria potentially not needed to define the clinical investigation population may unintentionally exclude specific subgroups
- Under diagnosis of disease etiologies and pathophysiology leading to under referral of demographic subgroups
- Avoidance of specific subgroups by investigators and Sponsors due to the perception that it takes more time and resources to recruit them
- Fear of fetal consequences (for female participants)
- Family responsibilities limiting women's ability to commit time for follow-up requirements

Historically, in the SPIRIT PRIME Long Lesion Registry (LLR), which was a US study to evaluate the safety and effectiveness of XIENCE PRIME (another XIENCE family of stent) in treatment of long coronary lesions, the study population had approximately 30-40% female and an average age of 64⁹. More than 8% of the patients in the SPIRIT PRIME LLR was non-white minority ethnicity.

As the SPIRIT 48 study will also enroll subjects in US, and has almost identical inclusion/exclusion criteria on the enrollment of female and minority ethnicity as for the SPIRIT PRIME LLR, Abbott expects similar proportions of female and minority ethnicity within US for the SIPRIT 48 study compared to SPIRIT PRIME LLR. The traditional barriers for female enrollment (such as fear or fetal consequence, family plan of having new babies that may limit the ability of time commitment to trial follow-up) are not applicable to the SIPRIT 48 study due to the expected average age of the patient population. Therefore, the eligibility criteria of the SIPRIT 48 study do not introduce gender or racial bias.

Abbott will take the following steps to ensure adequate representation of women and racial or ethnic minorities in this clinical investigation:

- Provide training to investigational site personnel to ensure adequate representation of these demographic subgroups
- Regularly review enrollment data to investigate whether there is under-representation of these demographic subgroups
- Regularly review withdrawal rates for under-represented subgroups and compare these rates with that in the overall clinical investigation population
- Retrain sites on the importance of recruiting and retaining subjects in the clinical investigation as appropriate and necessary
- Approach sites without bias or consideration for specific demographic subgroups
- Have informed consent materials in alternative languages and will work with sites and IRBs/ECs on recruitment materials

Clinical Investigation Plan

5.5 Subject Withdrawal

A subject is considered enrolled in the clinical investigation if signed informed consent is obtained.

Subjects who are withdrawn from the study will be followed (including AE reporting) until the time of withdrawal.

Subjects who are discontinued by site or the Sponsor will not be replaced.

Each registered subject shall remain in the clinical investigation until completion of the required follow-up period; however, a subject's participation in any clinical investigation is voluntary and the subject has the right to withdraw at any time without penalty or loss of benefit. Conceivable reasons for discontinuation may include, but not be limited to, the following:

- Subject voluntary withdrawal
- Subject is withdrawn by site or sponsor
- Subject lost-to follow-up as described below
- Subject's follow-up is terminated according to **Section 3.3 Suspension or Early Termination of the Clinical Investigation**.

The Sponsor must be notified of the reason(s) for subject withdrawal. The site will provide this information to the Sponsor. Investigators must also report this to their respective IRB/EC as defined by their institution's procedure(s).

No additional follow-up will be required or data recorded from subjects once withdrawn from the clinical investigation.

However, if a subject withdraws from the investigation due to problems related to the safety or performance of the device under investigation, the investigator shall ask for the subject's permission to follow his/her status/condition outside of the clinical investigation by means of mutual agreement.

In case of subject withdrawal of consent, the site should make attempts to schedule the subject for a final clinical investigation visit. At this final follow-up visit, the subject will undergo the following assessments:

- Review and report adverse events in electronic case report form (eCRF)
- Review and report protocol and concomitant medications in eCRF
- Complete subject reported outcomes in eCRF

Lost-to-Follow-up

If the subject misses two consecutive CIP-required follow-up visits and the attempts at contacting the subject detailed below are unsuccessful, then the subject is considered lost-to-follow-up. Site personnel shall make all reasonable efforts to locate and communicate with the subject (and document these efforts in the source documents), including the following, for CIP-required follow-up visits:

- A minimum of two telephone calls on different days during the specified follow-up windows to contact the subject should be recorded in the source documentation, including date, time and initials of site personnel trying to make contact.

Clinical Investigation Plan

- If these attempts are unsuccessful, a letter (certified if applicable) should be sent to the subject.
- If a subject misses one or more non-consecutive follow-up visits, those will be considered as missed visits. The subject may then return for subsequent visits. If the subject misses two consecutive follow-up visits and the above-mentioned attempts at communicating with the subject are unsuccessful, the subject will be considered lost-to-follow-up.

Note: Telephone contact with a General Practitioner, non-clinical investigation cardiologist or relative without the presence of the subject or indirect documentation obtained via discharge letters will not be considered as subject contact.

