6.5.1 Follow-up for All Subjects

Subjects registered in the clinical investigation will receive the following clinical follow-up:

- 1 month (30 ± 7 days): office visit/telephone contact (office visit is strongly recommended whenever possible)
- 6 months (180 ± 14 days): office visit/telephone contact (office visit is strongly recommended whenever possible)
- 12 months (365 ± 28 days): office visit (Note: a formal office visit is required at 12-month follow-up to ensure a thorough clinical evaluation. A telephone contact is an option *only* for subjects who would otherwise be lost to follow-up due to being unable to complete an office visit)
- 24 months (730 ± 28 days): office visit/telephone contact (office visit is strongly recommended whenever possible)

Clinical Investigation Plan

Clinical follow-up visits should be conducted by the investigator or trial personnel who have been trained to the protocol.

The following information will be collected at each of the time points:

- Any adverse events
- Use and compliance of protocol required antiplatelet medication
- Details of any subsequent coronary interventions (e.g., repeat PCI or CABG)

Note that information obtained through indirect contacts with a subject's healthcare provider or immediate family member will NOT be considered as a trial visit.

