8.4 Timing of Analysis

The primary analysis will be performed after database lock per FAS population when all subjects in FAS population have completed their primary endpoint follow-up visit.

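### The lost-to-follow-up rule, once calls and a letter have failed, lets a subject be discontinued from about day 194, with no requirement to attempt the 12-month contact that decides the primary endpoint

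*Protocol*

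**What the plan says.** Protocol 5.5 sets a two-part test: a subject who "misses two consecutive CIP-required follow-up visits and the attempts at contacting the subject detailed below are unsuccessful, then the subject is considered lost-to-follow-up". The attempts are specified: "A minimum of two telephone calls on different days during the specified follow-up windows to contact the subject should be recorded", and then "If these attempts are unsuccessful, a letter (certified if applicable) should be sent to the subject". No waiting period after the letter is given. The same section lists "Subject lost-to follow-up as described below" among the conceivable reasons for discontinuation. For subjects whose misses are not consecutive, it adds "The subject may then return for subsequent visits"; it has no matching sentence for consecutive misses.

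Protocol 6.5.1 schedules four contacts, at 30 ± 7, 180 ± 14, 365 ± 28 and 730 ± 28 days. The 12-month contact must be an office visit, with one exception: "A telephone contact is an option *only* for subjects who would otherwise be lost to follow-up due to being unable to complete an office visit". Protocol 8.4 times the primary analysis for "when all subjects in FAS population have completed their primary endpoint follow-up visit", and SAP 2.6 does the same.

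On missing outcomes, Protocol 8.7 and SAP 2.9 analyse available data only. SAP 2.2.3 censors event-free subjects at the last time they were known to be event-free. SAP 2.13 adds a tipping-point analysis for missing primary-endpoint data.

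**The concern.** The primary endpoint is TLF at 1 year, and the 12-month contact is the one that settles it. The loss rule is not tied to that contact. It can be met on the first two contacts alone, by someone who has not withdrawn consent, well before the endpoint is due. The telephone fallback in 6.5.1 exists to rescue subjects on the point of being lost at 12 months, but it need not be offered to someone already classed as lost at 6 months.

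What is at stake is avoidable missing primary data. A subject lost on the first pair may have no known event-free time after day 23, when the 1-month window opens, and so contributes little to a 1-year estimate. People who miss early contacts may also differ in risk from those who attend, for example in antiplatelet adherence or in being treated elsewhere. Leaving them out could then shift the TLF rate compared with the 20% goal, in a direction the documents do not allow one to predict.

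**Working it through.** **1. The plan's own figure.** Inputs from Protocol 8.3 and SAP 2.4: N = 107, true rate 10%, goal 20%, one-sided alpha 0.05, attrition 5%, power about 93% by simulation. The text naming the primary test is redacted, so I assumed a Kaplan-Meier 1-year rate with a Greenwood standard error, success being a one-sided 95% upper limit below 20%. With 20,000 runs per scenario, power was 91.7% to 93.7%, depending on when events and dropouts occur. The stated figure is reproduced. At assumed attrition of 10% and 15%, power was 90.6–92.4% and 89.6–91.8%, a modest fall.

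**2. Visit windows.** Window = target day ± allowance (Protocol 6.5.1).

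| Contact | Opens | Closes |
|---|---|---|
| 1 month | 30 − 7 = 23 | 30 + 7 = 37 |
| 6 months | 180 − 14 = 166 | 180 + 14 = 194 |
| 12 months | 365 − 28 = 337 | 365 + 28 = 393 |
| 24 months | 730 − 28 = 702 | 730 + 28 = 758 |

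**3. When each consecutive pair is complete.** I take a visit as missed when its window closes; this is the earliest reading.

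| Pair missed | Complete on | Relative to the 12-month window |
|---|---|---|
| 1 and 6 months | day 194 | 337 − 194 = 143 days before it opens; 393 − 194 = 199 days before it closes |
| 6 and 12 months | day 393 | as it closes |
| 12 and 24 months | day 758 | 758 − 393 = 365 days after it closes |

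Only the first pair can take a subject out before the endpoint contact is due.

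**4. The clauses together.** The rule names no pair; the status it confers is a listed reason for discontinuation; a return is stated only for non-consecutive misses; and no clause says that the 12-month contact must still be attempted for a subject classed as lost. Discontinuation before day 337 is therefore permitted, though not required.

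**5. Size.** Planned attrition is 0.05 × 107 = 5.35, about 5 subjects from all causes. The documents do not split this by cause, so the number lost through the first pair cannot be derived.

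To see whether a handful of outcomes could matter at all, take 107 − 5 = 102 evaluable subjects and the exact one-sided binomial test against 20%, which SAP 2.13 lists as a sensitivity analysis:

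- 13/102: p = 0.039 (pass). If 2 of the 5 missing had TLF, 15/107: p = 0.073 (fail).
- 14/102: p = 0.068 (fail). If all 5 were event-free, 14/107: p = 0.043 (pass).

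Under a one-sided 95% Wald upper limit, p̂ + 1.645 √(p̂(1 − p̂)/n), 14/102 gives 19.3% and 15/107 gives 19.5%. Both pass, so neither reversal above occurs. The Wald limit has its own edge: 15/102 gives 20.5% and 16/107 gives 20.6%, both failing. Any test has such a boundary; its existence says nothing about how many subjects this rule removes.

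**The case against.** The strongest reply is that the scenario is narrow. Missed visits alone are not enough: the calls and the letter must also fail. The 1-month and 6-month contacts may both be by telephone. The affected subject must therefore be unreachable for both and yet reachable at month 12. Day 194 is not a stated cutoff either: Protocol 3.1 says that a visit held outside its window is not a missed visit, and no section says when a visit becomes missed. This all stands, and it is why the point is limited to what can happen on the earliest reading.

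Four stronger readings are tempting, and the documents do not support them.

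- *The 12-month contact is never attempted for such a subject.* Nothing forbids it. Section 5.5 says registered subjects are to remain until follow-up is complete, and loss is only among the reasons that may lead to discontinuation. The sentence "No additional follow-up will be required or data recorded from subjects once withdrawn from the clinical investigation" speaks of withdrawn subjects and does not clearly cover lost ones. What can be said is that no clause requires the attempt.
- *It is a flaw that a missed 12-month visit alone does not make a subject lost.* Keeping that subject in the trial favours retention. Section 5.5 already attaches the calls and letter to each required visit, and 6.5.1 adds the telephone fallback at 12 months.
- *There is no route to events treated elsewhere.* Protocol 6.5.2 already requires efforts to obtain information on subjects treated at non-trial hospitals, and 10.9.4 lets the events committee review events identified by safety personnel.
- *The rule could decide the trial.* The illustrations above assign all planned attrition to this one rule and rest on a sensitivity test.

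The planned tipping-point analysis also counts in the plan's favour. It shows how far missing outcomes could change the conclusion, but it does not recover any of them.

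**Conclusion.** The point holds in a limited form. As written, section 5.5 permits a subject who has not withdrawn consent to be discontinued from about day 194, 143 days before the 12-month window opens, and does not require the 12-month contact to be attempted. This rests on two readings: that a visit counts as missed when its window closes, and that silence about a return after consecutive misses leaves discontinuation open.

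The number affected is unknown and probably small, some part of about 5 of 107. The power statement is not affected, and no effect on the trial's result can be inferred. The case for a change is that it removes an avoidable source of missing primary data, in a single-arm trial of modest size, at almost no cost.

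**What to change.** Amend the lost-to-follow-up text in Protocol 5.5 to state that:

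- missing earlier visits, consecutive or not, does not end participation;
- the 12-month contact sequence (calls, letter, telephone fallback) is attempted for every registered subject who has not died or withdrawn consent;
- such a subject may return at any time;
- loss to follow-up for the primary endpoint is declared only after the 12-month window has closed and those attempts have failed.

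The cost is a few sentences of protocol text and a few extra calls or letters for a handful of subjects. No visits or subjects are added, and the sample size and analysis are unchanged.
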